4.7.3.2. Caregiver Global Impression of Change (CGIC)

The CGIC comprises a single question to be rated on a 7-point scale: "Since the patient started treatment, please assess the status of the patient's overall condition (comparing their condition now to their condition before treatment) using the scale below."

The markers are: "Very Much Improved"; "Much Improved"; "Slightly Improved"; "No Change"; "Slightly Worse"; "Much Worse"; "Very Much Worse".

The caregiver will be asked to record the status of the patient's overall condition at Visit 2 (Day 1, prior to commencement of IMP) as a memory aid for subsequent visits.

The number and percentage of subjects in each response category will be presented by visit for both phases combined.

4.7.3.3. Physician Global Impression of Change (PGIC)

The PGIC comprises the same single question as the CGIC to be rated on the same, 7-point scale by the investigator. The investigator will be asked to record the status of the patients' overall condition at Visit 2 as a memory aid for subsequent visits.

The number and percentage of subjects in each response category will be presented by visit for both phases combined.

4.7.3.4. Vineland Adaptive Behavior Scales, Second Edition (Vineland-II)

The Vineland-II is an individually administered instrument for assessing adaptive behaviors and is widely used in pediatric clinical trials due to its applicability to children of all ages and developmental levels. The Vineland-II will be completed by the caregiver using a rating scale. Due to the possibility of cognitive/developmental delay, caregivers should start the assessment at the lowest age, irrespective of the patient's actual age. The Vineland-II consists of 5 domains (communication, daily living skills, socialization, motor skills, and maladaptive behavior) with items that are rated as 0=Never, 1=Sometimes or Partially, or 2=Usually. The Vineland-II scores will be calculated as the sum of all individual item scores across all scales.

Observed and change from baseline in Vineland-II scores will be summarized descriptively by visit for the OLE phase only.

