- Video-EEG (8–24 hours in duration).
- Clinical laboratory samples (blood and urine [if possible]) for:
 - Serum biochemistry.
 - Hematology.
 - Urinalysis.
- CGIC.
- PGIC.
- Caregiver diary review for:
 - Spasm/seizure information.
 - IMP usage.
 - Changes in concomitant AEDs.
 - Usage of rescue medication.
 - AEs.
- AEs.
- IMP compliance.
- IMP dispensing.

Visit 7 (Day 43 [±3 Days]); Visit 8 (Day 71 [±3 Days]); Visit 9 (Day 127 [±7 Days]); Visit 10 (Day 211 [±7 Days]); Visit 11 (Day 295 [±7 Days]); Visit 12 (Day 379 [±7 Days]): End of OLE Treatment/Withdrawal

The following will be collected/assessed at each of the above visits:

• Concomitant medication review.

EudraCT Number: 2015-004904-50

Protocol V3 20Sep16

Procedures (continued)

- Physical examination (including length [height], body weight, and head circumference).
- Vital signs (including supine blood pressure).
- ECG.
- Clinical laboratory samples (blood and urine [if possible]) for:
 - Serum biochemistry.
 - Hematology.
 - Urinalysis.
- CGIC.
- PGIC.
- Caregiver diary review for:
 - Spasm/seizure information.
 - IMP usage.
 - Changes in concomitant AEDs.
 - Usage of rescue medication.
 - AEs.
- AEs.
- IMP compliance.
- IMP dispensing (only if necessary at Visit 12).

The following will also be collected/assessed in addition to the above:

- Video-EEG (8–24 hours in duration) (Visits 7 and 9–12, or on withdrawal).
- Vineland-II (Visits 10 and 12, or on withdrawal).

Taper Period (10 Days)

Following end of treatment, discontinuation of IMP, or withdrawal, all patients will taper IMP (unless continued dosing is not possible due to an AE).

End of Taper Period Visit (+3 Days)

The following will be collected/assessed:

- Concomitant medication review.
- Physical examination (including length [height], body weight, and head circumference).
- Vital signs (including supine blood pressure).
- ECG.
- Clinical laboratory samples (blood and urine [if possible]) for:
 - Serum biochemistry.
 - Hematology.
 - Urinalysis.

Procedures (continued)

- Caregiver diary review for:
 - Spasm/seizure information.
 - IMP usage.
 - Changes in concomitant AEDs.
 - Usage of rescue medication.
 - AEs.
- AEs.
- IMP compliance.

Safety Follow-up Period (4 Weeks)

Following end of dosing (including taper period), all patients will commence a 4-week safety follow-up period, which includes weekly safety telephone calls followed by a safety follow-up visit.

Weekly Safety Telephone Calls (±3 Days)

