- If you have never seen the individual perform a behavior and don't know whether he or she performs it, circle "DK" for Don't Know.
- If an item has a Scoring Tip, use the tip to help you decide which response option to circle.
- If an item has a Scoring Tip that says you may circle "N/O" for No Opportunity, you may circle that option, if appropriate, instead of a "2," "1," "0," or "DK."
- Some sections do not apply to children younger than 3 years of age. If the child
 you are rating is younger than the age of the first start point, do not mark any items
 in that section.

Here is an example:

Continued on next page

2

EudraCT Number: 2015-004904-50

Protocol V3 20Sep16

Directions continued

If you want to change a response, mark an X through it, and circle your new choice.

If you have a question about any item, first mark the response that best describes the individual's behavior, and then circle the question mark (?) to the right of the response options.

Use the following table to help you choose the response that best describes the behavior of the individual you are rating.

RATING	THE INDIVIDUAL:
2 Usually	Usually performs the behavior without help or reminders when it is needed; or Performed the behavior at a younger age but now has outgrown it
1 Sometimes or Partially	Sometimes performs the behavior without help or reminders when it is needed; or Sometimes does it without help but sometimes needs help; or Sometimes does it without help but needs reminders; or Performs part of the behavior without help or reminders
0 Never	Never performs the behavior without help or reminders; or Never performs the behavior, because he or she is unable; or Never performs the behavior, because he or she is too young; or Never performs the behavior, because he or she is not allowed to; or Never performs the behavior, because he or she has a physical disability that prevents the behavior

Remember to respond in each section to every item after the start point for the individual's age.

EudraCT Number: 2015-004904-50

Protocol V3 20Sep16

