4.2.6. Subpopulations

No analyses of subgroups of subjects are planned.

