4.2.8. Missing, Unused, and Spurious Data

In general, there will be no substitutions made to accommodate missing data points. All data recorded on the CRF will be included in data listings that will accompany the clinical study report.

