6. CLINICAL STUDY REPORT APPENDICES

6.1. Planned Tables

- Table 1.1 Summary of Patient Disposition All Screened Subjects
- Table 1.2 Summary of Protocol Deviations All Enrolled Subjects
- Table 2.1 Summary of Demographic Data Safety
- Table 3.1 Summary of Previous Significant Non-Epilepsy Medical or Surgical History Now Resolved Safety
- Table 3.2 Summary of Significant Non-Epilepsy Medical or Surgical History Current Conditions Safety
- Table 4.1 Summary of Prior Antiepileptic Medications and Therapies Safety
- Table 4.2 Summary of Concomitant Antiepileptic Therapies Safety
- Table 4.3 Summary of Concomitant Antiepileptic Medications Safety
- Table 4.4 Summary of Concomitant Rescue Medications Safety
- Table 4.5 Summary of Other Concomitant Medications Safety
- Table 7.1 Summary of Exposure and Compliance to Study Treatment Pilot Phase Safety
- Table 7.2 Summary of Exposure and Compliance to Study Treatment OLE Phase Safety
- Table 8.1.1 Proportion of Treatment Responders Pilot Phase Safety
- Table 8.1.2 Proportion of Treatment Responders OLE Phase Safety
- Table 9.1.1 Proportion of Spasms and Seizure Subtypes by Caregiver Observation Pilot Phase Safety
- Table 9.1.2 Proportion of Spasms and Seizure Subtypes by Caregiver Observation OLE Phase Safety
- Table 9.2.1 Summary of CGIC Scores Pilot and OLE Phase Safety
- Table 9.2.2 Summary of PGIC Scores Pilot and OLE Phase Safety
- Table 9.3 Summary of Vineland Adaptive Behavior Scales Change from Baseline by Visit OLE Phase Safety
- Table 11.1.1 Overview of Adverse Events Pilot Phase Safety
- Table 11.1.2 Overview of Adverse Events OLE Phase Safety
- Table 11.2.1 Treatment-Emergent Adverse Events by System Organ Class and Preferred Term Pilot Phase Safety
- Table 11.2.2 Treatment-Emergent Adverse Events by System Organ Class and Preferred Term OLE Phase Safety
- Table 11.3.1 Treatment Related Treatment-Emergent Adverse Events by System Organ Class and Preferred Term Pilot Phase Safety
- Table 11.3.2 Treatment Related Treatment-Emergent Adverse Events by System Organ Class and Preferred Term OLE Phase Safety
- Table 11.4.1 Treatment-Emergent Adverse Events by System Organ Class and Preferred Term and Severity Pilot Phase Safety
- Table 11.4.2 Treatment-Emergent Adverse Events by System Organ Class and Preferred Term and Severity OLE Phase Safety
- Table 11.5.1 Treatment-Emergent Adverse Events by System Organ Class and Preferred Term and Sex Pilot Phase Safety

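### SAP 4.7.3.4 scores Vineland-II as one raw sum with no age reference, so Table 9.3 cannot show development relative to age; the sum also counts problem behaviors with the same sign as skills

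*SAP*

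**What the plan says.** SAP 4.7.3.4 holds the only scoring rule in either document: "The Vineland-II scores will be calculated as the sum of all individual item scores across all scales". The same section lists what goes into the sum: "The Vineland-II consists of 5 domains (communication, daily living skills, socialization, motor skills, and maladaptive behavior"). It describes all items as rated 0 = Never, 1 = Sometimes or Partially, 2 = Usually.

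The planned analysis reads: "Observed and change from baseline in Vineland-II scores will be summarized descriptively by visit for the OLE phase only". The output is "Table 9.3 Summary of Vineland Adaptive Behavior Scales Change from Baseline by Visit OLE Phase Safety". Neither document mentions a domain score, standard score, age equivalent or norm. SAP 4.2.4 plans no covariate adjustment, and SAP 4.2.6 states: "No analyses of subgroups of subjects are planned".

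Baseline is at Visit 2. The protocol synopsis (Procedures) then schedules "Vineland-II (Visits 10 and 12, or on withdrawal").

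Two completion instructions bear on the sum. Protocol 9.2.12.3 and SAP 4.7.3.4 tell caregivers to begin at the lowest age whatever the child's real age. The form in Protocol Appendix 3.3 says that if the child "you are rating is younger than the age of the first start point, do not mark any items" in that section.

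**The concern.** The OLE objective (Protocol 2.2.3, SAP 1.2.2.2) is to explore the effect on growth, adaptive behavior and development. In infants, a count of skills shown goes up simply because they get older. A mean change from baseline in such a count can look favorable while the children lose ground against their age. That is the outcome of interest here, since Protocol 3.1 says that 80–90% of children with infantile spasms have some degree of intellectual impairment.

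The rule also adds items that run the other way. On the form, Problem Behaviors items score 2 = Often, so more problems raise the same total that is meant to rise with better function.

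**Working it through.** The plan gives no figure for this endpoint, so there is none to reproduce. One month is taken as 30.4375 days.

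**1. Ageing over follow-up.** Visit 10 is 210 days and Visit 12 is 378 days after Visit 2, each ±7 days (Protocol 9.1.2.7 and 9.1.2.9).

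- Visit 10: 210 / 30.4375 = 6.9 months.
- Visit 12: 378 / 30.4375 = 12.4 months (371 days: 12.2; 385 days: 12.6).

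| Age at entry (months) | Age at Visit 12 (months) | Ratio |
|---|---|---|
| 1 (cohort 2 only) | 13.4 | 13.4 |
| 6 | 18.4 | 3.1 |
| 12 | 24.4 | 2.0 |
| 24 | 36.4 | 1.5 |

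One mean change pools these children. Those who withdraw are assessed earlier, so their intervals are shorter.

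**2. Direction of the adaptive items.** The form's directions say that the items run from infant to adult behaviors. Its rating table gives full credit (2) to a behavior the child once showed and has outgrown. The adaptive total is therefore built to accumulate.

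As an illustration with assumed rates (none is in the documents), a gain of r points per month gives r × 12.42 at Visit 12. For r = 2, 5 or 10 that is +25, +62 or +124 with no treatment effect. If 10 per month were typical for age, a child developing at half that pace would show 5 × 12.42 = +62 in Table 9.3 while falling (10 − 5) × 12.42 = 62 points further behind.

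**3. Items with the opposite sign.** Problem Behaviors has 11 + 10 + 15 + 14 = 50 items with start age 3+, a ceiling of 2 × 50 = 100 points. Section D also offers severe and moderate codes, for which the SAP gives no rule. Up to 10 days (7 + 3) can separate consent from Day 1.

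- Age limit followed, Visit 10: the oldest child is 24 + (217 + 10) / 30.4375 = 31.5 months, below 36, so no problem items are marked.
- Age limit followed, Visit 12: reaching 36 months needs an age at consent of 36 − (385 + 10) / 30.4375 = 23.0 to 36 − (371 + 1) / 30.4375 = 23.8 months, depending on visit timing.
- Every section completed: all 50 items enter the sum at baseline, Visit 10 and Visit 12.

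**4. Sections left blank below their start age.** Caring for Home (24 items) and Living in the Community (44 items) start at age 1. Under the age limit they are blank at baseline for infants under 12 months. They open at Visit 10 for those aged 12 − 6.9 = 5.1 months or more on Day 1, and by Visit 12 for every completer. What this does to the total depends on rules the SAP does not state:

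| Reading | Effect on the total |
|---|---|
| Age limit followed, blank counts as 0 | Close to that of a completed form, because the form scores 0 when a child is too young to perform a behavior |
| Age limit followed, blank makes the total missing | No spurious gain, but no baseline total for these infants |
| Every section completed | Item set constant; problem items counted at every visit |

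**The case against.** The strongest defense is that the SAP delivers what the protocol promised. The endpoint is change from baseline in Vineland-II score, the objective is exploratory, and neither document promises development relative to age. With 9 patients (SAP 4.1), having no covariates or subgroups is ordinary. Patient-level reading remains possible from Listing 8.2 (Vineland-II), Listing 3.1 (demographics) and Listing 1.3 (visit dates).

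This stands as a limit on the consequence, but it does not rescue the rule. A stated objective is to explore development, which a raw total in growing infants cannot show. Listing 8.2 is not said to give item or domain scores. Adding items of opposite direction is wrong wherever both are marked.

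Three stronger readings may tempt a reader, and the documents do not support them:

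- **That newly opened sections inflate the change substantially.** The two sections starting at age 1 hold 24 + 44 = 68 items, a ceiling of 136 points. A ceiling is not a bias. An infant too young for these items would score near 0 on them, so a blank counted as 0 loses almost nothing, and later points there are real skills. The mechanism vanishes if every section is completed.
- **That SAP 4.2.8 settles how blanks count.** Its statement "In general, there will be no substitutions made to accommodate missing data points" does not say that a blank adds 0; setting a blank to 0 could itself be called a substitution.
- **That better scoring would reveal a drug effect.** With one open-label arm, no scoring can isolate one.

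**Conclusion.** The point holds and is minor. SAP 4.7.3.4 states a wrong scoring rule rather than omitting a detail: as written, Table 9.3 cannot show development relative to age, and the total mixes items where higher is better with items where higher is worse. The second fault is narrow if the form's age limit is followed (Visit 12, entry at about 23 months or older) and general if every section is completed. The blank-section effect is probably small and its size cannot be settled from the documents.

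The conclusion rests on the form's construction. A rise with age is expected, not certain, since a child who plateaus or regresses may show none. Actual entry ages are not given, so the number of children crossing the 1-year or 3-year start points is unknown. No test or decision depends on this descriptive secondary endpoint.

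**What to change.** Revise SAP 4.7.3.4 and Table 9.3 as follows:

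1. Replace the all-scale sum with separate scores for communication, daily living, socialization and motor.
2. Make the instrument's age-referenced scores the main summary. If norms cannot be used, show raw domain totals per patient beside age at each visit, and state that change includes maturation and cannot be read as development relative to age.
3. Keep maladaptive items out of any adaptive total. Report them separately where age-applicable, with their own coding (2 = Often) and a rule for the Section D severity codes.
4. State how unmarked sections are scored, and that the lowest-age start instruction and the form's section age limit apply together, or which governs.

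Restricting each child to sections open at both baseline and follow-up would not be an adequate substitute: those totals would still rise with maturation, and pooled means would mix different item sets.

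The cost is SAP wording, programming, norm tables (the documents contain none) and some extra scoring work. The fallback in item 2 needs only item scores, age at informed consent (SAP 4.5) and visit dates (Listing 1.3). Date of birth is collected only where local rules allow (Protocol 9.2.3), so age at visit may be approximate for some children.

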4.8. Safety Analyses

Safety analyses will be conducted using the Safety Analysis Set.

4.8.1. Extent of Exposure and Compliance to Study Treatment

Descriptive statistics will be produced to describe the exposure and compliance to the IMP. The duration of exposure, and percent of treatment compliance will be summarized separately by phase.

Duration of exposure in the will be calculated for each subject by counting days where the study medication was actually taken (i.e., overall treatment duration - number of days a subject missed all doses of study medication). If a subject took at least one dose of study medication on a study day, then the subject will be counted as having received study medication on that day.

Overall percent compliance will be calculated and summarized as follows: duration of exposure / overall treatment duration x 100.

4.8.2. Adverse Events

Adverse events will be coded using the latest version of MedDRA and displayed in tables and listings using SOC and PT.

Analyses of AEs will be performed for those events that are considered treatment emergent AEs (TEAEs), where treatment emergent is defined as any adverse event that started, or worsened in severity or seriousness, following the first dose of IMP.

The number and percentage of subjects with the following AEs will be summarized:

- All-causality TEAEs
- Treatment-related TEAEs

- All-causality TEAEs by severity
- All-causality TEAEs by sex
- All-causality non-serious TEAEs
- All-causality serious TEAEs
- Treatment-related serious TEAEs
- TEAEs reported as leading to permanent cessation of study treatment
- Treatment-related TEAEs reported as leading to permanent cessation of study treatment
- Fatal TEAEs.

In these tabulations, each subject will contribute only once (i.e., the most related occurrence or the most intense occurrence) to each of the incidence rates in the descriptive analysis, regardless of the number of episodes. No formal hypothesis-testing analysis of adverse events incidence rates will be performed.

All adverse events occurring on study will be listed by cohort and subject. Listings will also be provided for the following: subject deaths; SAEs; and adverse events leading to withdrawal of study drug.

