9.1.2 Open-label Extension Phase

The OLE phase will last for a maximum of 1 year.

During the OLE phase, GWP42003-P may be discontinued by the investigator if:

EudraCT Number: 2015-004904-50

Protocol V3 20Sep16

• The patient has become spasm-free, as determined by clinical assessment by the investigator.

OR

• The patient is not perceived to be receiving any benefit from GWP42003-P, as determined by clinical assessment by the investigator.

For any patients who have their IMP discontinued by the investigator, the IVRS/IWRS will be contacted to confirm IMP discontinuation. All patients should commence the taper period, if possible (Section 9.1.3), and sufficient IMP will be dispensed if required.

If the investigator decides to discontinue GWP42003-P following resolution of spasms, the parent(s)/legal representative will be encouraged to allow the patient to remain in the trial to complete the remaining assessments. The investigator must contact the GW medical monitor to discuss the discontinuation process, including the subsequent assessments to be conducted.

If the investigator decides to discontinue GWP42003-P because the patient is not perceived to be receiving any benefit from GWP42003-P, the patient will **not** be asked to complete the remaining trial assessments and will be withdrawn from the trial as per Section 10 (withdrawal to be registered in the IVRS/IWRS).

Patients who have not demonstrated complete resolution of spasms but are perceived to be receiving some benefit from GWP42003-P may remain in the OLE and receive other concomitant medications during the OLE phase. The option of withdrawal from the trial will be discussed with the caregiver at each visit.

In cases of relapse, patients may restart IMP only if ALL of the following criteria are fulfilled:

- The patient had their IMP discontinued by the investigator due to resolution of spasms.
- The patient has remained in the trial to complete the remaining assessments.
- The decision to restart IMP is discussed with the GW medical monitor.

The IVRS/IWRS will then be contacted to confirm restart of IMP. Patients restarting IMP will re-titrate to their target dose of GWP42003-P and may continue at this dose, or the highest tolerated dose up to 40 mg/kg/day, for the remainder of the OLE phase. The next scheduled clinic visit will then be performed according to the Schedule of Assessments (APPENDIX 1).

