9.1.4 Safety Follow-up Period (4 Weeks)

Following end of dosing (including taper period), all patients will commence a 4-week safety follow-up period to ascertain the status of AEs continuing after cessation of IMP or any new AEs commencing after discontinuation. Patients who discontinue IMP during the OLE phase should begin the safety follow-up period following the end of the taper period. During the safety follow-up period, paper diary information will continue to be recorded.

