12 ADVERSE EVENT REPORTING

12.1 Definitions

12.1.1 Adverse Event

For the purposes of this trial an AE is defined as:

Any new unfavorable/unintended signs/symptoms (including abnormal laboratory findings when relevant), or diagnosis or worsening of a pre-existing condition, which occurs following screening (Visit 1) and at any point up to the post-treatment, safety follow-up visit, which may or may not be considered to be related to the IMP. Any event that is the result of a trial procedure must be recorded as an AE.

Surgical/Investigational procedures are not AEs. The medical reason for the procedure is the AE. Elective hospitalizations for pre-trial existing conditions or elective procedures are not AEs. The exception may be if the patient has an AE during hospitalization which prolongs their scheduled hospital stay in which case it would be considered a SAE (refer to Section 12.2).

If reporting a fatal event, the SAE term should be the underlying cause of the death (e.g., disease or medical condition leading to death).

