13.6.5.2 Adverse Events

AEs will be coded according to the Medical Dictionary for Regulatory Activities dictionary.

A TEAE is one that started, or worsened in severity or seriousness, following the first dose of IMP.

Descriptive presentations of TEAEs will be given by preferred term and system organ class for the safety analysis set for each phase of the trial separately. The number of patients reporting at least 1 TEAE will be provided.

The following summaries will be produced:

EudraCT Number: 2015-004904-50

Protocol V3 20Sep16

- All-causality TEAEs.
- Treatment-related TEAEs.
- All-causality TEAEs by severity.
- All-causality TEAEs by sex.
- All-causality serious TEAEs.
- Treatment-related serious TEAEs.
- TEAEs reported as leading to permanent cessation of study treatment.
- Treatment-related TEAEs reported as leading to permanent cessation of study treatment.
- Fatal TEAEs.

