2.5.1. Pilot Phase

- Safety as determined by AEs, clinical laboratory tests, ECG, vital signs and physical examinations during the treatment period
- The number and proportion of patients who are free of spasms and have resolution of hypsarrhythmia at the end of the 2-week treatment period, as determined by video-EEG.

2.5.2. *OLE Phase*

• To assess the long term safety as determined by AEs, clinical laboratory tests, ECG, vital signs and physical examinations during the treatment period.

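### The treatment-emergent definition has a start but no end, so OLE adverse event tables mix on-drug events with events in infants who stopped GWP42003-P for spasm freedom

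*SAP*

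**What the plan says.** SAP 4.8.2: "treatment emergent is defined as any adverse event that started, or worsened in severity or seriousness, following the first dose of IMP". Protocol 13.6.5.2 agrees: "A TEAE is one that started, or worsened in severity or seriousness, following the first dose of IMP". Both give a lower bound only.

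The OLE primary endpoint in SAP 2.5 is narrower: "To assess the long term safety as determined by AEs, clinical laboratory tests, ECG, vital signs and physical examinations during the treatment period". The SAP does not define that period.

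Protocol 9.1.2 lets the investigator stop IMP in the OLE for either of two reasons. If the reason is resolution of spasms, the parent or representative "will be encouraged to allow the patient to remain in the trial to complete the remaining assessments". If the reason is lack of perceived benefit, the infant is withdrawn and does not complete the later assessments. Protocol 13.6.1 ends the OLE evaluable period at the last assessment, not the last dose, so that data collected after a stop for spasm resolution are retained. Appendix 1 and SAP Table 1 list adverse events at every visit to Visit 12 (Day 379).

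SAP 4.8.1 measures exposure "by counting days where the study medication was actually taken". SAP 4.8.2 plans the number and percentage of subjects with each event on the OLE safety set. It plans no on-drug/off-drug split.

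**The concern.** Long-term safety is the OLE primary endpoint, and the TEAE and serious TEAE tables are its main display. A reader will take a treatment-emergent percentage to describe infants on the drug or shortly off it. Under the rule as written, an infection, an effect of another spasm therapy or an event of the underlying disease, arising months after the last dose, carries the same label as an event on full dose.

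The length of the window also depends on outcome. Two infants who stop at the same visit with equal exposure are treated differently. The one who became spasm-free can accrue events to Day 379. The one who did not benefit leaves after the taper and the 28-day follow-up. The OLE percentages combine these windows without saying so.

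**Working it through.** The plan states no figure on this point, so there is none to reproduce. The check is calendar arithmetic on the visit schedule.

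Inputs:
- OLE start, Day 15 (Visit 4), and last OLE visit, Day 379 (Visit 12): protocol 4.1 and Appendix 1.
- Taper, 10 days: protocol 9.1.3.
- Safety follow-up, 28 days after the final dose: protocol 9.1.4.2.
- Number of infants: 9 in the pilot phase (SAP 4.1), and only pilot patients in the trial (SAP 5). Nine is therefore an upper limit for the OLE; the number who entered it is not stated.
- Stop day *d*: not given. Assumed to fall on a scheduled visit, Visit 6 to Visit 11, with a full taper and no restart.

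Formulas: OLE length = 379 − 15 = 364 days. Last dose = *d* + 10. Off-drug days to Visit 12 = 379 − (*d* + 10). Days more than 28 days after the last dose = 379 − (*d* + 10 + 28) = 341 − *d*.

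| Assumed stop | *d* | Last dose | Off-drug days to Day 379 | Of these, beyond last dose + 28 | Share of 364 |
|---|---|---|---|---|---|
| Visit 6 | 29 | 39 | 340 | 312 | 86% |
| Visit 7 | 43 | 53 | 326 | 298 | 82% |
| Visit 8 | 71 | 81 | 298 | 270 | 74% |
| Visit 9 | 127 | 137 | 242 | 214 | 59% |
| Visit 10 | 211 | 221 | 158 | 130 | 36% |
| Visit 11 | 295 | 305 | 74 | 46 | 13% |

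For an infant withdrawn for lack of benefit, the corresponding figure is about zero, because contact ends with the follow-up visit 28 (+3) days after the last dose.

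Effect on a table: 1/9 = 11.1 percentage points per infant, and more if fewer than 9 entered the OLE. This applies only if the infant had no earlier on-drug event of the same term, because SAP 4.8.2 counts each subject once.

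Illustration only, with assumed background rates: for a stop at Visit 9, 214/30.44 = 7.03 months lie beyond the 28-day mark. The probability of at least one adverse event in that time is 1 − exp(−rate × 7.03). This gives 0.30, 0.50 and 0.88 at rates of 0.05, 0.1 and 0.3 per month.

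**The case against.** Following these infants off drug is a stated choice in protocol 13.6.1. An open, all-causality window is a defensible conservative approach to long-term safety in infants. It also gives those who stay roughly equal observation time, whereas a cut at 28 days with crude percentages shortens observation in early stoppers. The analysis is descriptive, treatment-related events are tabulated separately, and the subject listings would let a reader find off-drug events by hand. All of this stands. It argues for keeping the all-follow-up table, but does not explain why on-drug and off-drug events should go undistinguished in it.

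Three stronger readings are tempting, and the documents do not support them.

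- **That the exposure mismatch biases a rate.** Exposure counts dosed days while events are counted over all follow-up, but no exposure-adjusted rate is planned. The mismatch affects interpretation only.
- **That the protocol stops adverse event capture too early for these infants, so that events before a restart could be lost.** Protocol 12.1.1 does limit an adverse event to one "which occurs following screening (Visit 1) and at any point up to the post-treatment, safety follow-up visit", and 9.1.4 says "Patients who discontinue IMP during the OLE phase should begin the safety follow-up period following the end of the taper period". But 9.1.4.1 makes separate provision for infants who stay, with calls until the next clinic visit; Appendix 1 lists adverse events at each visit; and 9.2.13 requires a daily diary throughout. What remains is loose wording. Protocol 9.1.2 also leaves the later assessments to discussion with the medical monitor.
- **That incidence is known to be inflated.** The number of infants who stop for spasm freedom is not given and may be zero.

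**Conclusion.** The concern holds as a gap in classification. The TEAE definition has no end, the design deliberately creates off-drug follow-up for one group of stoppers, and the OLE tables do not separate the two kinds of event, although the endpoint is tied to the treatment period. The time affected is 312 days for an assumed stop at Visit 6, 298 at Visit 7 and 46 at Visit 11, per infant; it is zero if no infant stops for spasm freedom. With at most 9 infants, one infant with no earlier on-drug event of the term shifts its incidence by at least 11 points. These figures assume a full taper, no restart, continued attendance to Day 379 and adverse events recorded at each remaining visit. This should be changed, but it does not undermine the trial: the results are descriptive and no event is lost.

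**What to change.** In SAP 4.8.2, classify each OLE adverse event as:
- on-treatment: onset or worsening from the first OLE dose to 28 days after the last IMP dose including taper, with a new window if IMP is restarted; or
- off-treatment: onset or worsening after that.

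Tabulate the two separately for TEAEs and serious TEAEs. Keep the all-follow-up table so that the SAP stays consistent with protocol 13.6.1. Align protocol 13.6.5.2. The 28 days is the protocol's own follow-up length, so no new data are needed.

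The cost is one more set of descriptive tables. Crude on-treatment percentages will rest on shorter observation in infants who stop early, so show them beside exposure time.

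As a secondary step, reconcile protocol 12.1.1, 12.5 and 9.1.4 with 9.1.4.1 and Appendix 1, so that adverse event recording for infants who stop IMP but remain in the trial clearly runs to their last trial visit. This is a wording change.
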